6. HANDLING OF MISSING VALUES

No imputation for missing values will be performed.

7. STATISTICAL METHODOLOGY AND STATISTICAL ANALYSES

7.1. Statistical Methods

Mean, standard deviation, median, 1st quartile, 3rd quartile, inter-quartile range, minimum, and maximum will be provided when performing descriptive analysis of continuous data. Numbers and percentages will be provided when performing descriptive analysis of categorical data.

An unadjusted Kaplan Meier curve will be drawn to illustrate each time-to-event outcome. Medians and 95% confidence intervals obtained from the Kaplan-Meier curves will be reported.

All data analysis will be executed using statistical software SAS version 9.4 or later.

PFIZER CONFIDENTIAL

7.2. Statistical Analyses

Description of demographic, clinical, and treatment characteristics

Descriptive analyses will be conducted to evaluate the demographic, clinical, and treatment characteristics each of the study cohorts. Results will be reported in aggregate. Categorical variables (eg, ECOG performance status) will be reported as frequency and percentage. Continuous variables such as age will be reported as mean, standard deviation, median, 1st quartile, 3rd quartile, inter-quartile range, minimum, and maximum. In the case of missing observations, the number and percentage of missing values will be reported.

[figure not shown]
Description of effectiveness outcomes

For each of the study cohorts, real-world tumor response and response rate will be reported as frequency and percentage. Real-world progression-free survival, overall survival, time to first positive response, duration of response, duration of initial endocrine-based treatment, duration of all treatment, and Duration of follow-up will be assessed with the Kaplan-Meier method with 95% CIs, and summary tables of the number of events and censored patients. No covariates will be included. All missing values are excluded.

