16. ECOG/performance status, if available or indication of impaired performance status not otherwise classified as an ECOG rating, at index date (± 60 days). Where available, Karnofsky performance status will be converted to corresponding ECOG score.
17. Comorbidities, indicated as present vs. not indicated as present at index date. The conditions and date of the condition to be assessed will include those assessed as part of the standard Charlson Comorbidity Index. These include myocardial infarction, congestive heart failure, peripheral vascular disease, cerebrovascular accident, hemiplegia, chronic obstructive pulmonary disease, ulcer disease, diabetes, renal disease, connective tissue disease such as rheumatoid arthritis or lupus, Alzheimer's or other dementia, cirrhosis or other serious liver disease, leukemia, lymphoma, metastatic solid tumor (other than breast cancer), and HIV/AIDS.

PFIZER CONFIDENTIAL

18. Other comorbidities of interest, indicated as present vs. not indicated as present at index date: hypertension and hyperlipidemia.
19. Dates of disease progression after index date through the end of the record or the end of the study, whichever occurs first.
20. Documentation of treatment modifications (dose modification, schedule changes, dose delay, hold, or discontinuation) for palbociclib, **CCI** [REDACTED] and reasons for treatment modifications, if applicable, from the index date through the end of the record or the end of the study, whichever occurs first. Date of treatment modification and reason for modification will be collected, if available.
 - Reasons for modification will include: Cost, disease progression, patient refusal/request, toxicity (specify), other (specify), or UD.
21. Oral anti-cancer therapies. This will include all treatments from the index date through the end of the record or the end of the study, whichever occurs first. **CCI** [REDACTED]
22. Documentation of any IV, IM, or subcutaneous anti-cancer therapy not otherwise documented in standard medication tables, including all treatments received from the index date through the end of the record or the end of the study, whichever occurs first. Agent and start and end dates will be collected.

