9.3.3. Extracted Data

Patient data from OncoEMR will be flagged to be excluded from the regulatory study. Data extracted from the Definitive Oncology Dataset through SQL query will include the following:

1. Sex.
2. Insurance status (private only, public only, public and private, or neither) at index date and at initiation of the earliest endocrine-based regimen after the index date.
3. Date of birth.

[figure not shown]
4. Date of death, as indicated in the clinical record and by Social Security Death Index (SSDI) records or associated obituary records linked to the Definitive Oncology Dataset.
5. Treatments and dates of treatments for all infused or injected anti-cancer therapies from the index date through the end of the record or the end of the study, whichever occurs first.

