9.8. Quality Control

All data abstracted from the Definitive Oncology Dataset by CRNs will undergo an independent quality control review, with evaluation for consistency, completeness, and outlier values. This review is conducted by a supervising Curation Manager at Concerto HealthAI and through programmatic evaluation of study data. Data queries generated as part of quality review are documented and resolved, with documentation of queries and resolution maintained in a complete query log.

Data housed in electronic case report forms will then be exported to SAS datasets for data cleaning and preparation, creation of derived values, and preparation of analysis datasets. Data will then undergo initial statistical review, including examination of all fields for outlier values, and evaluation for internal consistency of study data. Values that are flagged as potentially anomalous during statistical review will be queried and resolved before analysis datasets are finalized. All study data also undergoes scientific review of study results prior to data lock.

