5.3. Efficacy/Effectiveness Endpoint(s)

Variable	Operational definition
Real-world progression-free survival	
Time in months from the initial endocrine-based therapy to the first progression or censoring date will be calculated.
 
For the purpose of this study, lines of therapy will be defined as the following Progression-based lines, in which a disease progression must occur for a new regimen to be interpreted as a new line of therapy.
 
Event: Any death or disease progression. Disease progression is taken to have occurred when a pathology report or radiological scan indicates disease progression and/or there is a physician progress note consistent with that determination. If patients did not die or have disease progression, they were censored at their last visit date during the study period for patients with only one line of therapy.

Overall survival	
Time in months from the initial endocrine-based therapy to death due to any cause or censoring date will be calculated.
 
Event: Any death recorded in the data extract. Patients who did not die will be censored at the time of data cutoff (assuming this is the last date the SSDI is searched).

Real-world tumor response	
Real-world tumor response (rwTR) will be assessed as best overall response for each regimen received within the initial endocrine-based therapy.
 
Responses will be classified as Complete response (CR); Partial response (PR); Stable disease (SD); Progressive disease (PD); Not evaluable (NE); or Undocumented. The date of the first positive response (CR or PR) and of the best overall response for each regimen will be collected.

Response rate	
The number of patients with complete response or partial response divided by the number of patients with at least one tumor assessment while on the initial endocrine-based therapy.

PFIZER CONFIDENTIAL

Time to first positive response	Months from the start date of the initial endocrine based therapy to the date of the first positive response (CR or PR).
Duration of response	Month from the date of the first positive response (CR or PR) to the date of first PD assessment or death. Patients without a PD assessment or death are censored at the the data cutoff date.
Duration of initial endocrine-based treatment	Months from the start date of the initial endocrine-based therapy to the end date of the initial endocrine-based therapy.

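### The SAP's no-imputation and exclude-missing rules make no exception for incomplete death or progression dates, so known events can drop out of rwPFS, OS and duration of response while event-free patients stay in.

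*SAP*

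**What the plan says.** SAP 6 is one sentence: "No imputation for missing values will be performed". SAP 7.2, in the paragraph on effectiveness outcomes analysed by Kaplan-Meier, adds: "No covariates will be included. All missing values are excluded". The table in SAP 7.2.2 marks missing data as excluded for all nine outcomes, including rwPFS, OS and duration of response.

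SAP 5.3 defines the end points of follow-up.
- **OS event:** "Event: Any death recorded in the data extract".
- **OS censoring:** "Patients who did not die will be censored at the time of data cutoff".
- **rwPFS censoring:** for patients with neither death nor progression, "they were censored at their last visit date during the study period".
- **Duration of response:** patients with neither PD nor death are censored at data cutoff.

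The dates come from routine records. Protocol 9.3.3 lists "Date of death, as indicated in the clinical record and by Social Security Death Index (SSDI) records", with linked obituary records as a further source. Protocol 9.3.2 has nurses abstract "Dates of disease progression after index date through the end of the record or the end of the study, whichever occurs first". Neither item states the precision of the date or a rule for a partial one.

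**The concern.** These Kaplan-Meier analyses are unadjusted, so no covariate can be missing. What can be missing is a part of the time itself: the start date or the end date. Event-free patients have an end date by definition (last visit or data cutoff). Patients with an event need a date taken from a chart, the SSDI or an obituary. Someone known to have died or progressed, but without a usable date, has no computable time. Under the stated rules that date may not be imputed, and the missing value is excluded.

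Such an exclusion depends on the outcome. rwPFS and OS are the main outcomes of primary Objective 2, and their medians are what will be reported. The loss would also be hard to see. The baseline shells have rows for missing values, but Tables 6a, 7a and 11a have lines only for events and censored patients. The commitment in SAP 7.2 to report numbers missing sits in the paragraph on demographic, clinical and treatment characteristics. No sensitivity analysis is planned.

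**Working it through.** **Follow-up, the plan's own figure.** Protocol 9.5 gives (50/2) + 8 = 33 months. From the dates, 2/3/2015 to 4/1/2019 is 49.9 months and 4/1/2019 to 12/1/2019 is 8.0 months, so 49.9/2 + 8.0 = 33.0. The figure is reproduced. Potential follow-up is taken as uniform from 8 to 58 months.

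**Illustrative medians, from Protocol 7.** 24.5 months for PFS; 38.5 and 60.1 months as the ends of the OS range. They are background figures, not design targets.

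**Assumptions.** Exponential event times. The share q of events without a usable date is not in the documents; 1% to 20% is assumed.

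**Why the direction is upward when dates are missing at random.** Let h be the true hazard and p(t) the chance that a patient at risk at time t goes on to an observed event. Deleting a random share q of events leaves (1 − q) of the events at t, and a risk set reduced by the factor 1 − q·p(t). The apparent hazard is

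h × (1 − q) / (1 − q·p(t)).

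Because p(t) < 1, this is below h, so survival looks better. At time zero, p(0) = 1 − (e^(−8λ) − e^(−58λ)) / (50λ) with λ = ln 2 / median. That is 0.573 for a 24.5-month median and 0.429 for 38.5. At q = 0.10:
- 24.5 months: ratio 0.9 / (1 − 0.0573) = 0.955; 24.5 / 0.955 = 25.7.
- 38.5 months: ratio 0.9 / (1 − 0.0429) = 0.940; 38.5 / 0.940 = 40.9.

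These are lower bounds, since p(t) shrinks as remaining follow-up shortens.

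**Simulation (1,000,000 patients), undated events deleted, dates missing at random:**

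| Share undated | True median 24.5 | True median 38.5 |
|---|---|---|
| 1% | 24.6 | 38.8 |
| 2% | 24.8 | 39.1 |
| 5% | 25.2 | 39.9 |
| 10% | 26.0 | 41.6 |
| 20% | 28.0 | 45.5 |

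With a true median of 60.1 months the median is not reached. True 36-month survival of 66.0% becomes 67.1%, 68.2% or 70.7% at 5%, 10% or 20%.

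**Dates not missing at random (true median 24.5; 5%, 10%, 20% of all events undated):**
- Only events before 12 months affected: 25.5, 26.6, 28.9.
- Only events after 24.5 months affected: 23.3, 22.3, 20.2. At 10%, 12-month survival falls from 71.3% to 69.5% while 48-month survival rises from 25.7% to 31.4%.

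The fall arises because deleting late events removes patients from the early risk set without removing any early event.

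**Keeping the events.** With 20% of events known only to the month and placed with an error of up to 0.5 month, the medians are 24.50 and 38.48. The same simulations with every date complete give 24.50 and 38.48.

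**The case against.** The strongest reply is that the defect is inferred. The SAP excludes missing values; it does not say that a patient with an undated event is deleted, or that a month-and-year date counts as missing. Nor do the documents say that incomplete event dates occur. Death dates have more than one source, and Protocol 9.8 provides independent review for completeness, adding: "Values that are flagged as potentially anomalous during statistical review will be queried and resolved before analysis datasets are finalized". The study is descriptive, with no hypotheses or decision rules.

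Most of this is fair, and it limits the claim. Deletion is the natural consequence of the text, not a stated rule, and the number affected may be small. But a query cannot supply a date the chart lacks, and Protocol 9.9 itself warns that some measurements may not be consistently available.

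A second reply is that Protocol 9.3.2 and 9.3.3 list dates of death and of progression after the index date with no separate event flag, whereas progression in the adjuvant setting is collected as yes/no plus a date. An undated event might then go unrecorded and the patient be censored. That is possible, but it does not rescue the plan. Under the same assumptions, with undated events at random treated as censored at cutoff, a 24.5-month median becomes 26.4 at 5% and 28.7 at 10%, and a 38.5-month median about 41 and 45. These are larger shifts than deletion gives. For rwPFS this is only indicative, because the SAP censors it at last visit.

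Not every exclusion is selective. A missing start or first-response date removes patients whether or not they later have the event. A patient with an undated progression may also stay in rwPFS through a later dated progression or death, which is a different error, also upward.

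**Conclusion.** The concern holds as a gap in the stated rules: with imputation barred and missing values excluded, nothing protects known deaths and progressions with incomplete dates, and no output would reveal their loss.

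A reader might infer that every survival estimate is lengthened. The documents do not support that. The direction depends on which events lose their dates: upward if missing at random or mainly early, but the median can fall if mainly late. The size depends on a share the documents do not give. At 1% to 2% missing at random, the shift is about 0.1 to 0.6 month across the two medians. At 10% it is about 1.5 months on 24.5 and 3.1 months on 38.5. All figures rest on exponential times and uniform entry. A bias of unknown size and direction in primary descriptive outcomes still calls for a rule fixed before results are seen.

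**What to change.** In SAP 6, 7.2 and 7.2.2, exempt event dates in the time-to-event outcomes from the no-imputation and exclusion rules. Leave the rule for tumor response and response rate as it is. Then state:

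1. Every patient with a known death or progression stays in the analysis, and event status is recorded separately from the date.
2. If only the day is missing, the event is placed mid-month, bounded by the last documented event-free contact and data cutoff.
3. If the month or the whole date is missing, the event is placed between the last event-free contact and the first record that states the event.
4. Tables 6a, 7a and 11a gain a line for the number of patients with an imputed date and the number excluded.
5. A sensitivity analysis repeats the estimates at the earliest and latest possible dates.

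The cost is a few sentences in the SAP, one event-status field and some date-handling code. The downside is an error of about two weeks for dates missing only the day and more for dates missing altogether; the sensitivity analysis bounds both.

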7.2.1. Safety Analyses

None.

PFIZER CONFIDENTIAL

7.2.2. Summary of Analyses of Efficacy/Effectiveness Outcomes

Outcome	Analysis Set(s)	Supports Protocol Objective Number	Missing Data
Real-world progression-free survival	All Eligible Patients Palbociclib + AI Patients CCI	2, 3	Excluded
Overall survival	All Eligible Patients Palbociclib + AI Patients CCI	2, 3	Excluded
Real-world tumor response	All Eligible Patients Palbociclib + AI Patients CCI	2, 3	Excluded
Response rate	All Eligible Patients Palbociclib + AI Patients CCI	2, 3	Excluded
Time to first positive response	All Eligible Patients Palbociclib + AI Patients CCI	2, 3	Excluded
Duration of response	All Eligible Patients Palbociclib + AI Patients CCI	2, 3	Excluded

PFIZER CONFIDENTIAL

Duration of initial endocrine based treatment	All Eligible Patients Palbociclib + AI Patients CCI [REDACTED]	1b	Excluded
Duration of all treatment	All Eligible Patients Palbociclib + AI Patients CCI [REDACTED]	1b	Excluded
Duration of follow-up	All Eligible Patients Palbociclib + AI Patients CCI [REDACTED]	1b	Excluded

PFIZER CONFIDENTIAL

8. REFERENCES**9. APPENDICES****9.1. APPENDIX 1: Table and Figure shells****Table 1a. Summary of Baseline Demographics – All Eligible Patients**

	All Eligible Patients (N=)
Age at A/MBC Diagnosis (years)	
Mean/SD	
N/Missing Values	
Min/Max	
First Quartile/Third Quartile	
Median/IQR	
Age Distribution (years), n (%)	
≤50	
51-64	
65 –74	
≥75	
Missing	
Sex, n (%)	
Female	
Male	
Missing	
Race, n (%)	
White	
Black	
Asian	
Other	
Unknown	
Missing	
Insurance Status, n (%)	
Private only	
Public only	
Public and Private	
Neither Public nor Private	
Missing	
Region of residence, n (%)	
Northeast	
Midwest	
South	
West	
Missing	

PFIZER CONFIDENTIAL

Table 1b. Summary of Baseline Demographics – Palbociclib + AI Patients

Repeat Table 1a for patients receiving Palbociclib with AI as initial endocrine-based therapy.

CCI

CCI	[REDACTED]
	[REDACTED]
	[REDACTED]
	[REDACTED]

Table 2a. Summary of Clinical Characteristics – All Eligible Patients

	All Eligible Patients (N=)
Number of Female Patients, n	
Menopausal Status, n (%) ^a	
Premenopausal	
Perimenopausal	
Postmenopausal	
Undocumented	
Missing	
Disease Stage at Initial Diagnosis, n (%)	
I	
II	
III	
IV	
Unknown/Undocumented	
Missing	
Disease Stage at Index Date, n (%)	
IIIB	
IIIC	
IV	
Missing	
Type of MBC	
De novo (Stage 4 at initial diagnosis)	
Recurrent (Stages 0-3 at initial diagnosis)	
Missing	
Time from Initial Diagnosis to First A/MBC Diagnosis	
Mean/SD	
N/Missing Values	
Min/Max	
First Quartile/Third Quartile	
Median/IQR	

PFIZER CONFIDENTIAL

Disease Histology, n (%) Adenoid Cystic Cribriform Ductal Inflammatory Intraductal Lobular Medullary with Lymphoid Stroma Medullary, NOS Mucinous Paget's Disease and Infiltrating Paget's Disease and Intraductal Papillary Secretory Squamous Cell Tubular Undifferentiated Undocumented Other, specify	
ECOG Performance Score ^b , n (%) 0 - Normal activity 1 - Symptoms demonstrated, but the patient remains ambulatory, and able to perform self-care 2 - Ambulatory >50% of the time and requires occasional assistance 3 - Ambulatory <50% of the time and requires nursing care 4 - Bedridden 5 - Death Missing	
Comorbidities, n (%) Myocardial infarction Congestive heart failure Peripheral vascular disease Cerebrovascular accident Hemiplegia Chronic obstructive pulmonary disease Ulcer disease Diabetes Renal disease Connective tissue disease Alzheimer's or other dementia Cirrhosis or other serious liver disease Leukemia Lymphoma	

PFIZER CONFIDENTIAL

Metastatic solid tumor (other than breast cancer) HIV/AIDS Hypertension Hyperlipidemia	
Modified Charlson Comorbidity Index ^c Mean/SD N/Missing Values Min/Max First Quartile/Third Quartile Median/IQR	
Sites of distant metastasis, n (%) Bone Chest wall Contralateral breast Distant lymph node(s) Liver Lung Peritoneum Pleural nodules Malignant pleural effusion Skin Brain Undocumented Other, specify	
Number of Metastatic Sites Mean/SD N/Missing Values Min/Max First Quartile/Third Quartile Median/IQR	
Visceral Metastasis ^d Yes No Missing	
Non-visceral Metastasis ^e Yes No Missing	
Bone-only Metastasis ^f Yes No Missing	
Modalities of Treatment, n (%) Surgery Radiation	

PFIZER CONFIDENTIAL

Chemotherapy	
Hormone therapy	
Missing	
Disease Free Interval (months)	
Mean/SD	
N/Missing Values	
Min/Max	
First Quartile/Third Quartile	
Median/IQR	
Endocrine Sensitivity, n (%)	
Sensitive	
Resistant	
Refractory	
Missing	
Endocrine Resistance, n (%)	
Primary	
Secondary	
Missing	

^a Percentage is based on the number of female patients.

^b Karnofsky performance status is converted to corresponding ECOG score

^c Weighting of comorbid conditions (not including breast cancer) will follow the weighting as specified in the Charlson Comorbidity Index.

^d Visceral: metastasis at one or more of the following sites: liver, pancreas, intestines, lung, heart, malignant pleural effusion, peritoneum, pleura. Other metastasis sites, including bone or non-visceral metastasis, may be present.

^e Non-visceral: metastasis at one or more of the following sites: bone, brain, skin, chest wall, contralateral breast, or distant lymph nodes.

^f Bone only: Bone metastasis, with no metastasis at any other identified site.

Table 2b. Summary of Clinical Characteristics – Palbociclib + AI Patients

Repeat Table 2a for patients receiving Palbociclib with AI as initial endocrine-based therapy.

CCI

Table 3a. Summary of Treatment Regimen Duration – All Eligible Patients

		Treatment Regimen Duration (months)				
		n	%	Mean	SD	Median
Line 1	Regimenx	XXX	XXX	XXX	XXX	XXX
	Regimeny	XXX	XXX	XXX	XXX	XXX
	Regimenz	XXX	XXX	XXX	XXX	XXX
	...	XXX	XXX	XXX	XXX	XXX
Line 2	Regimenx	XXX	XXX	XXX	XXX	XXX
	Regimeny	XXX	XXX	XXX	XXX	XXX
	Regimenz	XXX	XXX	XXX	XXX	XXX
	...	XXX	XXX	XXX	XXX	XXX
Line 3	Regimenx	XXX	XXX	XXX	XXX	XXX
	Regimeny	XXX	XXX	XXX	XXX	XXX
	Regimenz	XXX	XXX	XXX	XXX	XXX
	...	XXX	XXX	XXX	XXX	XXX

Lines of therapy are progression-based and are restricted to the first 3 lines.

Table 3b. Summary of Treatment Regimen Duration – Palbociclib + AI Patients

Repeat Table 3a for patients receiving Palbociclib with AI as initial endocrine-based therapy.

[figure not shown]
CCI

Table 4a. Summary of Treatment Sequencing Duration – All Eligible Patients

	Treatment Sequence	Duration (month)				
		n	%	Mean	SD	Median
One line	Line 1 Regimenx	XXX	XXX	XXX	XXX	XXX
	Line 1 Regimeny	XXX	XXX	XXX	XXX	XXX
	Line 1 Regimenz	XXX	XXX	XXX	XXX	XXX
	...	XXX	XXX	XXX	XXX	XXX
Two lines	Line 1 Regimen ==> Line 2 Regimen	XXX	XXX	XXX	XXX	XXX
	Line 1 Regimen ==> Line 2 Regimen	XXX	XXX	XXX	XXX	XXX
	Line 1 Regimen ==> Line 2 Regimen	XXX	XXX	XXX	XXX	XXX
	...	XXX	XXX	XXX	XXX	XXX

PFIZER CONFIDENTIAL

Three lines	Line 1 Regimen ==> Line 2 Regimen ==> Line 3 Regimen	xxx	xxx	xxx	xxx	xxx
	Line 1 Regimen ==> Line 2 Regimen ==> Line 3 Regimen	xxx	xxx	xxx	xxx	xxx
	Line 1 Regimen ==> Line 2 Regimen ==> Line 3 Regimen	xxx	xxx	xxx	xxx	xxx
	...	xxx	xxx	xxx	xxx	xxx

Lines of therapy are progression-based and are restricted to the first 3 lines.

Table 4b. Summary of Treatment Sequencing Duration – Palbociclib + AI Patients

Repeat Table 4a for patients receiving Palbociclib with AI as initial endocrine-based therapy.

CCI

Repeat Table 4a for patients receiving Abemaciclib with AI as initial endocrine-based therapy.

Table 5a. Palbociclib Dosing Information

	Palbociclib (N=)
Starting Dose, n (%)	
Dose level 1	
Dose level 2	
Dose level 3	
End Dose, n (%)	
Dose level 1	
Dose level 2	
Dose level 3	
Palbociclib Treatment Status, n (%)	
Treatment Ongoing	
Treatment Discontinued	
Duration of Palbociclib Treatment (months)	
Mean/SD	
N/Missing Values	
Min/Max	
First Quartile/Third Quartile	
Median/IQR	
Duration of Palbociclib Treatment (months)	
<6	

PFIZER CONFIDENTIAL

6 – 12 13 – 24 25 – 36 >36	
Reason for Discontinuing Palbociclib Therapy, n (%) Cost Disease Progression Patient Refusal/Request Toxicity, specify Other, specify Undocumented	
Time to Dose Discontinuation Mean/SD N/Missing Values Min/Max First Quartile/Third Quartile Median/IQR	
Dose Adjustments, n (%) Dose Reduced 125mg – 100mg 125mg – 75mg 100mg – 75mg Dose Increased 75mg – 100mg 75mg – 125mg 100mg – 125mg	
Number of Patients Starting at 125 mg, n (%) Dose Reduced, n (%) ^a	
Type of Dose Adjustments Dose Modification Schedule Changes Dose Delay Hold Discontinuation	
Time to First Dose Adjustment Mean/SD N/Missing Values Min/Max First Quartile/Third Quartile Median/IQR	

^a Percentage is based on number of patients who start at 125 mg of Palbociclib.

[figure not shown]

Table 6a. Summary of Real-world Progression-free Survival – All Eligible Patients

	All Eligible Patients (N=)
Number of Real-world Progression Events, n (%)	
Number Censored, n (%)	
Kaplan-Meier Estimates of Time to Event (months)	
Median (95% CI)	

PFIZER CONFIDENTIAL

Table 6b. Summary of Real-world Progression-free Survival - Palbociclib + AI Patients

Repeat Table 6a for patients receiving Palbociclib with AI as initial endocrine-based therapy.

CCI

[figure not shown]

Table 7a. Summary of Overall Survival – All Eligible Patients

	All Eligible Patients (N=)
Number of All-cause Mortality, n (%)	
Number Censored, n (%)	
Kaplan-Meier Estimates of Time to Event (months)	
Median (95% CI)	

Table 7b. Summary of Overall Survival - Palbociclib + AI Patients

Repeat Table 7a for patients receiving Palbociclib with AI as initial endocrine-based therapy.

CCI

Table 8a. Summary of Real-world Tumor Response – All Eligible Patients

	All Eligible Patients (N=) n (%)
Regimenx	
Complete Response	
Partial Response	
Stable Disease	
Progressive Disease	
Not Evaluable	
Undocumented	
Regimeny	
Complete Response	
Partial Response	
Stable Disease	

PFIZER CONFIDENTIAL

Progressive Disease	
Not Evaluable	
Undocumented	
Regimenz	
Complete Response	
Partial Response	
Stable Disease	
Progressive Disease	
Not Evaluable	
Undocumented	
...	

Real-world tumor response (rwTR) will be assessed as best overall response for each regimen received within the initial endocrine-based therapy.

Table 8b. Summary of Real-world Tumor Response – *Palbociclib + AI Patients*

Repeat Table 8a for patients receiving Palbociclib with AI as initial endocrine-based therapy.

CCI

Table 9a. Summary of Response Rate – All Eligible Patients

	All Eligible Patients (N=) n (%)
Regimenx	
Regimeny	
Regimenz	
...	

Response rate is calculated as the number of patients with complete response or partial response divided by the number of patients with at least one tumor assessment while on the initial endocrine-based therapy.

Table 9b. Summary of Response Rate – *Palbociclib + AI Patients*

Repeat Table 9a for patients receiving Palbociclib with AI as initial endocrine-based therapy.

CCI

PFIZER CONFIDENTIAL

Table 10a. Time to First Positive Response - All Eligible Patients

	All Eligible Patients (N=)
Number of Positive Response, n (%)	
Number Censored, n (%)	
Kaplan-Meier Estimates of Time to Event (months)	
Median (95% CI)	

Table 10b. Time to First Positive Response - Palbociclib + AI Patients

Repeat Table 10a for patients receiving Palbociclib with AI as initial endocrine-based therapy.

CCI

